7.2.5.2.1 Survival Follow-Up

Once a subject experiences confirmed disease progression or starts a new anti-cancer therapy, the subject moves into the Survival Follow-Up phase and should be contacted by telephone every 12 weeks to assess for survival status until death, withdrawal of consent, or the end of the study, whichever occurs first. Survival Follow ends for all patients when the last treated patient on study completes the Follow-Up Phase (end of study).

7.3 Assessing and Recording Adverse Events

An adverse event is defined as any untoward medical occurrence in a patient or clinical investigation subject administered a pharmaceutical product and which does not necessarily have to have a causal relationship with this treatment. An adverse event can therefore be any unfavorable and unintended sign (including an abnormal laboratory finding, for example), symptom, or disease temporally associated with the use of a medicinal product or protocol-specified procedure, whether or not considered related to the medicinal product or protocol-specified procedure. Any worsening (i.e., any clinically significant adverse change in frequency and/or intensity) of a preexisting condition that is temporally associated with the use of the Merck's product, is also an adverse event.

Changes resulting from normal growth and development that do not vary significantly in frequency or severity from expected levels are not to be considered adverse events. Examples of this may include, but are not limited to, teething, typical crying in infants and children and onset of menses or menopause occurring at a physiologically appropriate time.

Merck product includes any pharmaceutical product, biological product, device, diagnostic agent or protocol-specified procedure, whether investigational (including placebo or active comparator medication) or marketed, manufactured by, licensed by, provided by or distributed by Merck for human use.

Adverse events may occur during the course of the use of Merck product in clinical trials or within the Follow-Up period specified by the protocol, or prescribed in clinical practice, from overdose (whether accidental or intentional), from abuse and from withdrawal.

Adverse events may also occur in screened subjects during any pre-allocation baseline period as a result of a protocol-specified intervention, including washout or discontinuation of usual therapy, diet, placebo treatment or a procedure.

All adverse events will be recorded from the time the consent form is signed through 30 days following cessation of treatment and at each examination on the Adverse Event case report forms/worksheets. The reporting timeframe for adverse events meeting any serious criteria is described in [section 7.3.3.1](#).

Adverse events will not be collected for subjects during the pre-screening period (for determination of archival tissue status) as long as that subject has not undergone any protocol-specified procedure or intervention. If the subject requires a blood draw, fresh tumor biopsy etc., the subject is first required to provide consent to the main study and AEs will be captured according to guidelines for standard AE reporting.

7.3.1 Definition of an Overdose for This Protocol and Reporting of Overdose to the Principal Investigator and to Merck

For purposes of this trial, an overdose will be defined as any dose exceeding the prescribed dose for pembrolizumab by 20% over the prescribed dose. No specific information is available on the treatment of overdose of pembrolizumab. In the event of overdose, pembrolizumab should be

discontinued and the subject should be observed closely for signs of toxicity. Appropriate supportive treatment should be provided if clinically indicated.

If an adverse event(s) is associated with (“results from”) the overdose of a Merck product, the adverse event(s) is reported as a serious adverse event, even if no other seriousness criteria are met.

If a dose of Merck’s product meeting the protocol definition of overdose is taken without any associated clinical symptoms or abnormal laboratory results, the overdose is reported as a non-serious Event of Clinical Interest (ECI), using the terminology “accidental or intentional overdose without adverse effect.”

All reports of overdose with and without an adverse event must be reported within 24 hours to the Principal Investigator and within 2 working days to Merck Global Safety. (Attn: Worldwide Product Safety; [contact])

7.3.2 Reporting of Pregnancy and Lactation to the Sponsor and to Merck

Although pregnancy and lactation are not considered adverse events, it is the responsibility of investigators or their designees to report any pregnancy or lactation in a subject (spontaneously reported to them), including the pregnancy of a male subject's female partner that occurs during the trial or within 120 days of completing the trial completing the trial, or 30 days following cessation of treatment if the subject initiates new anticancer therapy, whichever is earlier. All subjects and female partners of male subjects who become pregnant must be followed to the completion/termination of the pregnancy. Pregnancy outcomes of spontaneous abortion, missed abortion, benign hydatidiform mole, blighted ovum, fetal death, intrauterine death, miscarriage and stillbirth must be reported as serious events (Important Medical Events). If the pregnancy continues to term, the outcome (health of infant) must also be reported.

Such events must be reported within 24 hours to the Principal Investigator and within 2 working days to Merck Global Safety. (Attn: Worldwide Product Safety; [contact])

7.3.3 Immediate Reporting of Adverse Events to the Principal Investigator and to Merck

7.3.3.1 Serious Adverse Events

A serious adverse event is any adverse event occurring at any dose or during any use of Merck’s product that:

- Results in death;
- Is life threatening;
- Results in persistent or significant disability/incapacity;
- Results in or prolongs an existing inpatient hospitalization;
- Is a congenital anomaly/birth defect;
- Is a new cancer (that is not a condition of the study);
- Is associated with an overdose;
- Is another important medical event

Refer to Table 7 for additional details regarding each of the above criteria.

Progression of the cancer under study is not considered an adverse event unless it results in hospitalization or death.

Any serious adverse event, or follow up to a serious adverse event, including death due to any cause other than progression of the cancer under study that occurs to any subject from the time the consent is signed through 90 days following cessation of treatment, or the initiation of new anti-cancer therapy, whichever is earlier, whether or not related to Merck product, must be reported within 24 hours to the Sponsor and within 2 working days to Merck Global Safety.

Non-serious Events of Clinical Interest will be forwarded to Merck Global Safety and will be handled in the same manner as SAEs.

Additionally, any serious adverse event, considered by an investigator to be related to Merck product that is brought to the attention of the investigator at any time outside of the time period specified in the previous paragraph also must be reported immediately to the Principal Investigator and to Merck.

SAE reports and any other relevant safety information are to be forwarded to the Merck Global Safety [contact]

A copy of all 15 Day Reports and Annual Progress Reports is submitted as required by FDA, European Union (EU), Pharmaceutical and Medical Devices agency (PMDA) or other local regulators. Investigators will cross reference this submission according to local regulations to the Merck Investigational Compound Number (IND, CSA, etc.) at the time of submission.

Additionally investigators will submit a copy of these reports to Merck & Co., Inc. (Attn: Worldwide Product Safety; [contact]) at the time of submission to FDA.

All subjects with serious adverse events must be followed up for outcome.

7.3.3.2 Events of Clinical Interest

Selected non-serious and serious adverse events are also known as Events of Clinical Interest (ECI) and must be recorded as such on the Adverse Event case report forms/worksheets and reported within 24 hours to the Principal Investigator and within 2 working days to Merck Global Safety. (Attn: Worldwide Product Safety; [contact])

Events of clinical interest for this trial include:

1. An overdose of Merck product, as defined in [Section 7.3.1](#) - Definition of an Overdose for This Protocol and Reporting of Overdose to the Sponsor, that is not associated with clinical symptoms or abnormal laboratory results.
2. An elevated AST or ALT lab value that is greater than or equal to 3X the upper limit of normal and an elevated total bilirubin lab value that is greater than or equal to 2X the upper limit of normal and, at the same time, an alkaline phosphatase lab value that is less than 2X the upper

limit of normal, as determined by way of protocol-specified laboratory testing or unscheduled laboratory testing.*

***Note:** These criteria are based upon available regulatory guidance documents. The purpose of the criteria is to specify a threshold of abnormal hepatic tests that may require an additional evaluation for an underlying etiology.

1. Additional adverse events:

A separate guidance document has been provided entitled “Event of Clinical Interest Guidance Document” (previously entitled, “Event of Clinical Interest and Immune-Related Adverse Event Guidance Document”). This document provides guidance regarding identification, evaluation and management of ECIs and irAEs.

ECIs (both non-serious and serious adverse events) identified in this guidance document from the date of first dose through 90 days following cessation of treatment, or 30 days after the initiation of a new anticancer therapy, whichever is earlier, need to be reported within 24 hours to the Sponsor and within 2 working days to Merck Global Safety. (Attn: Worldwide Product Safety; [contact]), regardless of attribution to study treatment, consistent with standard SAE reporting guidelines.

Subjects should be assessed for possible ECIs prior to each dose. Lab results should be evaluated and subjects should be asked for signs and symptoms suggestive of an immune-related event. Subjects who develop an ECI thought to be immune-related should have additional testing to rule out other etiologic causes. If lab results or symptoms indicate a possible immune-related ECI, then additional testing should be performed to rule out other etiologic causes. If no other cause is found, then it is assumed to be immune-related.

7.3.4 Evaluating Adverse Events

An investigator or qualified designee will evaluate all adverse events according to the NCI Common Terminology for Adverse Events (CTCAE) v5.0. Any adverse event which changes CTCAE grade over the course of a given episode will have each change of grade recorded on the adverse event case report forms/worksheets.

All adverse events regardless of CTCAE grade must also be evaluated for seriousness.

Table 7 Evaluating Adverse Events

An investigator or qualified designee will evaluate all adverse events as to:

CTCAE Grading	Grade 1	Mild; asymptomatic or mild symptoms; clinical or diagnostic observations only; intervention not indicated.
	Grade 2	Moderate; minimal, local or noninvasive intervention indicated; limiting age-appropriate instrumental ADL.
	Grade 3	Severe or medically significant but not immediately life-threatening; hospitalization or prolongation or hospitalization indicated; disabling; limiting self-care ADL.
	Grade 4	Life threatening consequences; urgent intervention indicated.
	Grade 5	Death related to AE
Seriousness	A serious adverse event is any adverse event occurring at any dose or during any use of Merck product that: †Results in death; or †Is life threatening; or places the subject, in the view of the investigator, at immediate risk of death from the event as it occurred (Note: This does not include an adverse event that, had it occurred in a more severe form, might have caused death.); or †Results in a persistent or significant disability/incapacity (substantial disruption of one's ability to conduct normal life functions); or †Results in or prolongs an existing inpatient hospitalization (hospitalization is defined as an inpatient admission, regardless of length of stay, even if the hospitalization is a precautionary measure for continued observation. (Note: Hospitalization [including hospitalization for an elective procedure] for a preexisting condition which has not worsened does not constitute a serious adverse event.); or †Is a congenital anomaly/birth defect (in offspring of subject taking the product regardless of time to diagnosis); or Is a new cancer; (that is not a condition of the study) or Is an overdose (whether accidental or intentional). Any adverse event associated with an overdose is considered a serious adverse event. An overdose that is not associated with an adverse event is considered a non-serious event of clinical interest and must be reported within 24 hours. Other important medical events that may not result in death, not be life threatening, or not require hospitalization may be considered a serious adverse event when, based upon appropriate medical judgment, the event may jeopardize the subject and may require medical or surgical intervention to prevent one of the outcomes listed previously (designated above by a †).	
Duration	Record the start and stop dates of the adverse event. If less than 1 day, indicate the appropriate length of time and units	
Action taken	Did the adverse event cause the Merck product to be discontinued?	
Relationship to test drug	Did the Merck product cause the adverse event? The determination of the likelihood that the Merck product caused the adverse event will be provided by an investigator who is a qualified physician. The investigator's signed/dated initials on the source document or worksheet that supports the causality noted on the AE form, ensures that a medically qualified assessment of causality was done. This initialed document must be retained for the required regulatory time frame. The criteria below are intended as reference guidelines to assist the investigator in assessing the likelihood of a relationship between the test drug and the adverse event based upon the available information. The following components are to be used to assess the relationship between the Merck product and the AE; the greater the correlation with the components and their respective elements (in number and/or intensity), the more likely the Merck product caused the adverse event (AE): Exposure Is there evidence that the subject was actually exposed to the Merck product such as: reliable history, acceptable compliance assessment (pill count, diary, etc.), expected pharmacologic effect, or measurement of drug/metabolite in bodily specimen? Time Course Did the AE follow in a reasonable temporal sequence from administration of the Merck product? Is the time of onset of the AE compatible with a drug-induced effect (applies to trials with investigational medicinal product)? Likely Cause Is the AE not reasonably explained by another etiology such as underlying disease, other drug(s)/vaccine(s), or other host or environmental factors	

Relationship to Merck product (continued)	The following components are to be used to assess the relationship between the test drug and the AE: (continued)	
	Dechallenge	Was the Merck product discontinued or dose/exposure/frequency reduced? If yes, did the AE resolve or improve? If yes, this is a positive dechallenge. If no, this is a negative dechallenge. (Note: This criterion is not applicable if: (1) the AE resulted in death or permanent disability; (2) the AE resolved/improved despite continuation of the Merck product; or (3) the trial is a single-dose drug trial); or (4) Merck product(s) is/are only used one time.)
Rechallenge	Was the subject re-exposed to the Merck product in this study? If yes, did the AE recur or worsen? If yes, this is a positive rechallenge. If no, this is a negative rechallenge. (Note: This criterion is not applicable if: (1) the initial AE resulted in death or permanent disability, or (2) the trial is a single-dose drug trial); or (3) Merck product(s) is/are used only one time). NOTE: IF A RECHALLENGE IS PLANNED FOR AN ADVERSE EVENT WHICH WAS SERIOUS AND WHICH MAY HAVE BEEN CAUSED BY THE MERCK PRODUCT, OR IF REEXPOSURE TO THE MERCK PRODUCT POSES ADDITIONAL POTENTIAL SIGNIFICANT RISK TO THE SUBJECT, THEN THE RECHALLENGE MUST BE APPROVED IN ADVANCE BY THE U.S. CLINICAL MONITOR AS PER DOSE MODIFICATION GUIDELINES IN THE PROTOCOL.	
		The assessment of relationship will be reported on the case report forms /worksheets by an investigator who is a qualified physician according to his/her best clinical judgment, including consideration of the above elements.
Record one of the following		Use the following scale of criteria as guidance (not all criteria must be present to be indicative of a Merck product relationship).
Yes, there is a reasonable possibility of Merck product relationship.		There is evidence of exposure to the Merck product. The temporal sequence of the AE onset relative to the administration of the Merck product is reasonable. The AE is more likely explained by the Merck product than by another cause.
No, there is not a reasonable possibility Merck product relationship		Subject did not receive the Merck product OR temporal sequence of the AE onset relative to administration of the Merck product is not reasonable OR there is another obvious cause of the AE. (Also entered for a subject with overdose without an associated AE.)

7.3.5 Sponsor Responsibility for Reporting Adverse Events

All Adverse Events will be reported to regulatory authorities, IRB/IECs and investigators in accordance with all applicable global laws and regulations.

8.0 DATA AND SAFETY MONITORING

8.1 Safety Requirements

At any time during the conduct of the trial, if it is the opinion of an investigator that the risks to the patient warrant early closure of the study, this recommendation should be made in writing to the Principal Investigator.

8.1.1 Accrual and Study Progress Oversight

The Principal Investigator will direct the formation of a Safety Data Review Board (SDRB) that will review study accrual and provide direction for dose escalations based on analysis of collected safety data including AE's, SAE's and DLT's. The SDRB will consist of the Principal Investigator, designated sub-investigators, and study administrative staff. Meetings will occur after completion of each dose-level cohort and on an as needed basis to address unanticipated adverse events. Meeting minutes will be documented. Any significant safety findings will be reported to Fred Hutch/University of Washington Cancer Consortium Institutional Review Board (IRB).

8.1.2 Data Monitoring

Institutional support of trial monitoring will be in accordance with the Fred Hutch/University of Washington Cancer Consortium Institutional Data and Safety Monitoring Plan (DSMP). Under the provisions of this plan, Fred Hutch Clinical Research Support coordinates data and compliance monitoring conducted by consultants, contract research organizations, or Fred Hutch employees unaffiliated with the conduct of the study. Independent monitoring visits occur at specified intervals determined by the assessed risk level of the study and the findings of previous visits per the institutional DSMP.

In addition, protocols are reviewed at least annually and as needed by the Consortium Data and Safety Monitoring Committee (DSMC), Fred Hutch Scientific Review Committee (SRC) and the Fred Hutch/University of Washington Cancer Consortium Institutional Review Board (IRB). The review committees evaluate accrual, adverse events, stopping rules, and adherence to the applicable data and safety monitoring plan for studies actively enrolling or treating patients. The IRB reviews the study progress and safety information to assess continued acceptability of the risk-benefit ratio for human subjects. Approval of committees as applicable is necessary to continue the study.

The trial will comply with the standard guidelines set forth by these regulatory committees and other institutional, state and federal guidelines.

8.1.3 Auditing

All trials conducted at UW/SCCA are subject to audit by the institution or any regulatory authority.

8.2 Records

Case Report Forms (CRFs) for individual patients will be provided by the Principal Investigator.

8.3 Source Documents

Source documents provide evidence for the existence of the patient and substantiate the integrity of the data collected. Source documents are filed at the investigator's site.

All data entered in CRF's that are transcribed from source documents must be consistent with the source documents or the discrepancies must be explained. The investigator may need to request previous medical records or transfer records.

8.4 Direct Access to Source Data and Documents

The investigator and institution will permit study-related monitoring, audits, EC review and regulatory inspection, providing direct access to all related source data / documents. The study is monitored under the Cancer Consortium Data and Safety Monitoring Plan (DSMP) which details the full scope and extent of monitoring and provides for immediate action in the event of the discovery of major deviations. CRFs and all source documents, including progress notes and copies of laboratory and medical test results, must be available at all times for review by the clinical study monitor, auditor and inspection by health authorities (e.g. FDA).

9.0 STATISTICAL ANALYSIS PLAN

9.1 Statistical Analysis Plan

The primary objective of this study is to evaluate the safety of IL-2 in combination with pembrolizumab. Statistical analysis will be descriptive for observed toxicities.

The secondary objective is to evaluate clinical outcomes (CR, PR, ORR, DCR, PFS) in comparison to historical data among advanced RCC patients treated with HD IL-2 or anti-PD1 monotherapies. The target enrollment for a conditional expansion cohort will be exploratory in nature, and no predictive statistical analysis has been applied.

Progression-free survival will be defined from the time of registration to progression or death. Patients last known to be alive and progression-free will be censored at the date of their last disease assessment. PFS will be evaluated using the method of Kaplan-Meier. Median PFS times and associated 95% confidence interval will also be calculated.

Exploratory objectives include the evaluation of the PD-1 pathway. For this objective, PD-1 pathway protein expression measures will be correlated with clinical outcomes. Specifically, the

association between pre-treatment PD-L1 expression by IHC, TIL density and T cell subset identification for CD4+, CD8+ and Treg cells, and peripheral blood analysis to quantify lymphocyte subsets including CD4+/CD8+/Treg and overall response will be compared using logistic regression. In addition, the association between end of cycle peripheral blood re-analysis to quantify lymphocyte subsets including CD4+/CD8+/Treg and PFS will be evaluated using a Cox proportional hazards model, among patients alive and progression-free at end of treatment. Similarly, the association between PD-L1 expression by IHC and TIL density and T cell subset identification for CD4+, CD8+ effector and Treg cells at the end of treatment and PFS will be evaluated among patients who do not achieve a CR but are also progression-free and the end of treatment.

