1.0 TRIAL SUMMARY

Abbreviated Title	IL-2 and Pembrolizumab for Advanced RCC
Trial Phase	Phase I
IND Number	133532
Clinical Indication	Advanced or metastatic clear cell RCC
Trial Type	Therapeutic
Type of control	Historical control
Route of administration	SQ IL-2; IV IL-2 IV pembrolizumab
Trial Blinding	None
Treatment Groups	Dose Level 1: SQ IL-2 plus IV pembrolizumab; Dose Levels 2 and 3: IV IL-2 plus IV pembrolizumab
Number of trial subjects	N=12 to 15
Estimated Enrollment Period	36 months
Estimated duration of trial	5 years
Duration of Participation	Maximum of 3 cycles of treatment (36 weeks) with follow-up.

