2.0 TRIAL DESIGN

2.1 Trial Design

This is a phase I, open-label, dose escalation and conditional cohort expansion at the maximum tolerated dose (MTD) of Interleukin-2 (IL-2; aldesleukin), a soluble cytokine growth factor for T lymphocytes, in combination with pembrolizumab (MK-3475), a humanized monoclonal antibody (mAb) of the IgG4/kappa isotype designed to target the Programmed Death 1 (PD1) membrane receptor on activated T lymphocytes. Treatment is for patients with advanced or metastatic clear cell renal cell carcinoma (RCC).

The study will consist of 3 periods: Screening (up to 28 days), Treatment (up to three 12-week courses), and Follow-Up (up to 1 year). Each treatment course (“course” nomenclature is by the conventions of IL-2 treatment) is comprised of 4 doses (cycles) of pembrolizumab given by iv infusion every 3 weeks combined with 1 cycle of IL-2 given by SQ administration daily 5 days/week for 6 weeks at Dose Level 1; or by IV bolus infusion (Dose Level 2 and 3) every 8 hours to a maximum of 14 doses on weeks 1 (cycle 1) and 4 (cycle 2) of a treatment course. Investigator tumor response assessment (by RECIST v1.1) must be completed before the first dose of the next treatment course. The maximum number of on-study treatment courses will be three.

Following completion of treatment, patients with ongoing disease control (CR, PR, or SD) will enter Surveillance Follow-Up. Disease status will be reassessed every 3 months for up to 1-year duration. Patients with disease control completing one year of Surveillance Follow-Up or patients with disease progression will enter Survival Follow-Up to study completion.

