4.2.4.2 Secondary Endpoint - Efficacy

The efficacy objective of this trial is to evaluate the anti-tumor activity of pembrolizumab plus IL-2 in subjects with advanced RCC. Responses will be evaluated by RECIST 1.1. Best overall response rate (ORR) to include complete responders (CR) and partial responders (PR); disease control rate (DCR = CR+PR+stable disease, SD), and progression free survival (PFS) for patients treated with IL-2 combined with pembrolizumab will be collected and analyzed by cohort and for all treated patients. Outcomes will be compared to historical data for RCC patients treated with IL-2 or anti-PD-1 as monotherapy.

Immunotherapeutic agents may produce antitumor effects by potentiating endogenous cancer-specific immune responses which may be functionally anergic. The response patterns seen with such an approach may extend beyond the typical time course of responses seen with cytotoxic agents, and can manifest a clinical response after an initial increase in tumor burden or even the appearance of new lesions. In subjects who have initial evidence of radiological PD following a first course of treatment, it is at the discretion of the investigator whether to continue a subject on study treatment for a second treatment course. This decision should be based on the clinical judgment of the subject's overall clinical condition, including performance status, clinical symptoms, laboratory data, and tolerance for study treatments.

Subjects recommended to receive a second treatment course after PD should meet the following criteria:

- Absence of signs and symptoms indicating disease progression
- Absence of progressive tumor at critical anatomical sites (e.g., cord compression) requiring urgent alternative medical intervention
- Absence of rapid progression of disease
- No decline in ECOG performance status

This allowance takes into account the observation that some subjects can have a transient tumor flare in the first few months after the start of immunotherapy, but with subsequent disease response.

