5.2.1.2 Rules for Dose Escalation

Dose-limiting toxicities (DLT's) observed in course 1 will be used to determine escalation to the next dose level. A course is 12 weeks. The study will use a 3 + 3 trial design for IL-2 dose escalation. The first 3 patients will be enrolled at Dose Level 1. If no dose-limiting toxicities (DLT's) occur in the first 3 patients over treatment course 1, Dose Level 2 will then open for enrollment of the next 3 patients. In the absence of DLT's in three patients treated at Dose Level 2, then Dose Level 3 will open for enrollment of the next 3 patients.

If 1 of 3 subjects in a cohort experiences a DLT, the Cohort will expand to 6 pts. If only 1 of 6 patients experiences a DLT with all patients followed for safety endpoints to the end of course 1, then the next cohort dose level will open to enroll.

If two or more patients in a cohort experience a DLT, that dose level exceeds the MTD.

If two or more delayed DLT's (i.e., DLT's that occur after course 1) are noted within a dose-escalation cohort, accrual will be held pending safety analysis by the Principal Investigator and Merck and restarted only with Principal Investigator and Sponsor approvals with IRB and FDA notification.

Dose escalations or de-escalations of pembrolizumab are not allowed. Treatment delays for toxicity are allowable as described in [Section 5.2.1.4](#). Patients enrolled into Dose Level 3 who require treatment interruption and meet restarting criteria as described in [Section 5.2.1.4](#) may have IL-2 dosing de-escalated to the IV IL-2 Dose Level 2 for the subsequent treatment cycle and/or course(s) 2 and/or 3. Individual patient IL-2 dosing cannot be escalated.

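### Section 9.1 counts deaths as PFS events without time limit but censors survivors at their last assessment; if imaging ends after one year, late deaths alone decide the Kaplan-Meier tail

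*Combined protocol and SAP*

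**What the plan says.** Section 9.1 defines PFS from registration to progression or death and sets no limit on the time between the last assessment and a death. For survivors it says: "Patients last known to be alive and progression-free will be censored at the date of their last disease assessment". PFS is summarised by Kaplan-Meier, with a median and 95% confidence interval. Under Section 4.2.4.2 the efficacy outcomes "will be collected and analyzed by cohort and for all treated patients" and are set against historical data.

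The documents disagree on when imaging ends.

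- **One-year limit.** Section 2.1: "Disease status will be reassessed every 3 months for up to 1-year duration", and then "Patients with disease control completing one year of Surveillance Follow-Up or patients with disease progression will enter Survival Follow-Up to study completion". Flow chart footnote 3 agrees. Section 7.2.2.5 ties post-treatment imaging to patients still in Surveillance Follow-Up.
- **No stated limit.** Section 5.6 follows disease status until progression, other cancer treatment, withdrawal or loss to follow-up. Section 7.2.5.2 continues to new therapy, progression, death or end of study. Section 7.2.5.2.1 moves a patient to Survival Follow-Up on confirmed progression or new therapy, and does not mention completing one year.

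In Survival Follow-Up patients "should be contacted by telephone every 12 weeks to assess for survival status". This contact ends for everyone when the last treated patient completes follow-up.

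**The concern.** Under the one-year limit, deaths and survivors are observed for different lengths of time. A progression-free patient who survives leaves the risk set, in retrospect, at the last scan. A patient with the same scans who dies two years later stays in the risk set until that death. Being at risk beyond the last scans then depends on the future outcome, which is informative censoring.

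The tail is where this shows. The protocol's background stresses durable, unmaintained remissions after IL-2, so a plateau is a result of interest, and this rule can turn one into 0%. Dose levels open in sequence: after three patients without a DLT, "Dose Level 2 will then open for enrollment of the next 3 patients". Earlier levels therefore have longer telephone-only follow-up and are more exposed.

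**Working it through.** The plan states no PFS target or event count, so there is no figure to reproduce.

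**Timeline under the one-year limit**

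- Treatment lasts at most 36 weeks (Section 1.0: "Maximum of 3 cycles of treatment (36 weeks) with follow-up"), and surveillance adds 52 weeks: 36 + 52 = 88 weeks, about 20.2 months, taking treatment to start at registration.
- Scans every 12 weeks after week 36 fall at weeks 48, 60, 72 and 84. The last is at about 19.3 months.
- Enrolment lasts 36 months (Section 1.0). If the study ends when the last patient reaches week 88, the first patient has up to 36 months of telephone-only follow-up and the last has none.

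**Worked cases (assumed data)**

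The estimate is multiplied by (1 − deaths or progressions / number at risk) at each event time. The median is the first time at which it is 50% or less.

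- *Case A, 12 patients.* Five progress on scans: 7/12 = 58.3%. Five of the other seven are censored at week 84, leaving two at risk. Death at month 30: 58.3% × 1/2 = 29.2%. Death at month 40: 0%. Median 30 months. Stopped at week 88: 58.3%, median not reached.
- *Case B, 12 patients.* Eight progress: 4/12 = 33.3%. Two are censored at week 84 and two die at months 30 and 40: 16.7%, then 0%. The sixth progression, at the week-48 scan, sets the median at 11.0 months with or without the stop. Only the tail changes.
- *Case C, one dose level of 6.* Two progress: 4/6 = 66.7%. Three are censored at week 84 and one dies at month 30: 0%, median 30 months. Stopped at week 88: 66.7%, median not reached.
- *Counter-case.* In Case A, suppose one of the seven stopped after course 1, had a last scan at week 60 and died at week 70. Six others are still being scanned, so 58.3% × 6/7 = 50.0%, an ordinary step.

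**Simulation (all rates assumed)**

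Inputs: N = 12 or 15; uniform accrual over 36 months; one-year limit; study end at last enrolment + 88 weeks. Median time to progression among progressors is 7.2, 11 or 15.1 months (7.2 and 15.1 are the lowest and highest median PFS values quoted in Section 4.1.5). The share that never progresses is 5% or 12% (complete response rates quoted in Sections 4.1.2 and 4.2.1, used as stand-ins), or 30% as an upper value. Median survival after progression is 12 or 24 months, death without progression 0 or 0.3% per month, and 0 or 30% of patients stop early.

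Trials in which the curve ends at zero:

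| Never progress | Section 9.1 as written | Same rule, stopped at week 88 |
|---|---|---|
| 5–12% | 30–85% | 0–13% |
| 30% | 20–79% | 0–2% |

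True month-36 PFS is p + (1 − p) × 2^(−36/m), times exp(−0.003 × 36) = 0.898 where deaths without progression occur.

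- 5–12% never progress: lowest (0.05 + 0.95/32) × 0.898 = 7%; highest 0.12 + 0.88 × 0.192 = 29%.
- 30% never progress: lowest (0.30 + 0.70/32) × 0.898 = 29%; highest 0.30 + 0.70 × 0.192 = 43%.

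With 15 patients split 3/6/6 in order of enrolment and the same true PFS, Level 2 ended at zero in 20–68% of trials and Level 3 in 5–45%. The difference was 12.6 to 37.7 percentage points across scenarios.

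**The case against.** **Imaging may continue to study end.** Sections 5.6 and 7.2.5.2 can be read that way. Under that reading the written rule still ended at zero in 14–48% of simulated trials (5–12% never progress) and 3–13% (30%). Those are largely ordinary small-sample endings, so ending at zero is an imperfect measure of harm. This stands, and the point is conditional on the one-year limit.

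**The event definition is not shown to be wrong.** Nearly all the gain comes from where the curve stops. This also stands. A reader might infer that deaths should count only within one scan interval of the last assessment, 84 + 7 = 91 days. Adding that limit to the week-88 stop gave 0–14% and 0–4% ending at zero, no better than the stop alone, and the medians differed in at most 6% of trials. It could also do harm. Section 5.2.1.3 makes a delay a DLT only beyond 21 days, so on-study scans can be 84 + 21 + 7 = 112 days apart, and a death on treatment between days 92 and 112 would be dropped.

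**An assessment need not be a protocol scan.** Section 9.1 says disease assessment, and progression might become known in other ways after scheduled imaging. The simulation allows none of this, so its rates are towards the upper end. This stands in part: the documents schedule no disease assessment in Survival Follow-Up.

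**Late deaths are legitimate events.** They are, if survivors are observed as long. Under the one-year limit they are not.

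**The study may end sooner.** If it ended only 12 weeks after the last enrolment, the written rule gave 10–40% and 7–30%.

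**Conclusion.** The point holds as a conditional one and is worth a cheap correction. If imaging ends one year after treatment, Section 9.1 followed exactly can report 0% where 33–67% were progression-free at the last scans (Cases A to C). The mechanism is arithmetic; how often it would occur rests on assumed rates.

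A reader might infer more than the documents support.

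- That the curve is bound to end at zero. It does so only under the one-year limit, and only if the last death falls after every other patient's last scan.
- That the median is generally wrong. It is at risk when more than half of patients are progression-free as imaging ends; Case B shows it unchanged.
- That dose selection or safety is compromised. PFS is secondary and descriptive, and no test or decision rule uses it. It is analysed by cohort, but no comparison between cohorts is planned.

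**What to change.** 1. Reconcile Sections 2.1, 5.6, 7.2.5.2, 7.2.5.2.1 and flow chart footnote 3 on when surveillance imaging ends.
2. If it ends at one year, add to Section 9.1:

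> PFS curves, medians and confidence intervals are estimated only up to the end of scheduled imaging (at most about week 88 from registration), with numbers at risk. Follow-up beyond that time is administratively censored for PFS. Deaths up to that time without recorded progression count as events; later deaths are reported as overall survival. A sensitivity analysis counts all deaths. Patients with no post-baseline assessment who are alive are censored at registration.

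The last sentence is needed because a baseline scan may be up to 6 weeks old (flow chart footnote 17) and could precede registration.

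**Cost.** A few sentences in Section 9.1 and an amendment aligning four sections and one footnote. Under the one-year reading no extra patients, scans or data are needed; choosing imaging to study end would add scans.

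**Downside.** Late deaths leave the main PFS estimate, and a median not reached becomes more common. In simulation a finite median was reported in 54–100% of trials instead of 83–100% (5–12% never progress), and in 24–87% instead of 60–96% (30%). Those figures combine the week-88 stop with the 91-day limit, which changed medians little.

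**What remains.** A death between the week-84 scan and week 88 still counts with few at risk. So does a death before week 88 in a patient who stopped after course 1, whose imaging ends at about 12 + 52 = 64 weeks. Numbers at risk will show this.
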